13.2 Tumor assessment by iRECIST (secondary endpoints)

To account for the possible unique pattern of immune-mediated tumor responses, evaluation by iRECIST will also be performed as secondary objectives. Below is a general summary of the iRECIST criteria. Please refer to Seymour et al. 2017 for the full iRECIST guidelines.⁶⁰ Responses assigned under iRECIST are designated with the prefix 'i' (immune).

13.2.1 Similarities and differences between iRECIST and RECIST v1.1

In iRECIST, the definitions are identical to RECIST v1.1 for the following:

- Measurable and non-measurable disease including nodal disease
- Numbers and sites of target lesions
- Calculation of sum of diameters (SoD)
- CR, PR, SD, duration
- Confirmation of CR or PR (for non-randomized trials)
- PD for target and non-target lesions

However, the management of new lesions and determination of progression differ:

- For target lesions, the first PD by RECIST v1.1 is iUPD (immune unconfirmed PD).
- iUPD must be confirmed 4-8 weeks later by imaging.
 - o iCPD (immune confirmed PD) is established if there is a further increase in SoD of target disease from iUPD of at least 5mm.
 - o If there is subsequent iPR, iCR, or iSD (determined by RECIST v1.1 compared to baseline), then the iUPD date is ignored and the status is reset.
 - o If there is no change detected from iUPD, then the timepoint response remains iUPD

- Treatment past iUPD is considered only if the patient is clinically stable.
- iUPD can be assigned multiple times as long as iCPD is not confirmed at the next assessment.
- Assignment of non-target lesions follows similar rules.
- New target lesions are recorded separately and not included in SoD of target lesions identified at baseline; the sum of diameters for the new target lesions is determined.
 - o Appearance of new lesions results in iUPD, which requires confirmation at 4-8 weeks.
 - o iCPD is assigned if, on next imaging, additional new lesions appear, there is an increase in new lesions (at least 5mm), or appearance of new lesions.

13.2.2 Timepoint response using iRECIST

Target lesions	Non-target lesions	New lesions	Timepoint response with no previous iUPD in any category ¹	Timepoint response with previous iUPD in any category
iCR	iCR	No	iCR	iCR
iCR	Non-iCR/ non-iUPD	No	iPR	iPR
iPR	Non-iCR/ non-iUPD	No	iPR	iPR
iSD	Non-iCR/ non-iUPD	No	iSD	iSD
iUPD with no change, or with decrease from last timepoint	iUPD with no change, or decrease from last timepoint	Yes	Not applicable	New lesions confirm iCPD if new lesions were previously identified and have increased in size (≥ 5 mm in the sum of diameters for new lesion target or any increase for new lesion non-target) or number; if no change is seen in new lesions (size or number) from last timepoint, assignment remains iUPD
iSD, iPR, iCR	iUPD	No	iUPD	Remains iUPD unless iCPD is confirmed by a further increase in size of non-target disease (does not need to meet RECIST v1.1 criteria for unequivocal progression)
iUPD	Non-iCR/ non-iUPD, or iCR	No	iUPD	Remains iUPD unless iCPD is confirmed by a further increase in SoD ≥ 5 mm; otherwise, assignment remains iUPD
iUPD	iUPD	No	iUPD	Remains iUPD unless iCPD is confirmed by a further increase in previously identified target lesion iUPD in SoD ≥ 5 mm or non-target lesion iUPD
iUPD	iUPD	Yes	iUPD	Remains iUPD unless iCPD is confirmed by a further increase in previously identified target lesion iUPD in SoD ≥ 5 mm, previously identified non-

				target iUPD, or increase in size of number of new lesions previously identified
Non-iUPD or progression	Non-iUPD or progression	Yes	iUPD	Remains iUPD unless iCPD is confirmed by increase in size or number of new lesions previously identified

Adapted from Seymour et al. 2017.⁶⁰

¹Previously identified in assessment immediately before this timepoint.

Target lesions, non-target lesions, and new lesions defined according to RECIST v1.1. In the absence of pseudoprogression, RECIST v1.1 and iRECIST categories for CR, PR, SD would be the same.

Abbreviations: “I” indicates immune responses assigned using iRECIST; iCR, complete response; iPR, partial response; iSD, stable disease; iUPD, unconfirmed progressive disease; non-iCR/non-iUPD, criteria for neither CR nor PD have been met; iCPD, confirmed progressive disease; RECIST, Response Evaluation Criteria in Solid Tumors.

13.3 Methods of measurement

Imaging-based evaluation is required for assessment of response to study treatment. The same imaging modality must be used throughout the study to measure disease.

Imaging: Only CT or MRI are acceptable forms of imaging for response assessment. Conventional CT and MRI should be performed with cuts of 5 mm or less in slice thickness contiguously. This applies to tumors of the chest, abdomen and pelvis. Head and neck tumors and those of extremities usually require specific protocols. All other forms of assessment, including chest x-ray, ultrasound, PET without diagnostic CT, and endoscopy, will not be used for disease measurement.

As per NCCN guidelines for the management of hepatocellular carcinoma, it is recommended that disease assessment be performed using multiphasic contrast CT or MRI of abdomen/pelvis, as well as CT chest with or without contrast. As clinically indicated, bone scan and contrast-imaging of neck may be obtained to monitor disease.

(Principles of Imaging, NCCN guidelines version 1.2019, Hepatocellular Carcinoma, https://www.nccn.org/professionals/physician_gls/pdf/hepatobiliary.pdf)

Alpha fetoprotein (AFP): AFP may be elevated in patients with hepatocellular carcinoma and/or cirrhosis. AFP should be obtained at screening for all patients. If abnormal at baseline, it should be obtained on Cycle 1 Day 1, and every 3 cycles afterwards until treatment discontinuation.

Cytology and histology: Cytologic confirmation of the neoplastic nature of any effusion that appears or worsens during treatment is required when the measurable tumor has met response or stable disease criteria.

Clinical examination: Clinically detected lesions will only be considered measurable when they are superficial (e.g. skin nodules, palpable lymph nodes). For skin lesions, documentation by color photography, including a ruler to estimate size of the lesion, is recommended. Photographs should be retained at the institution.

14.0 DRUG INFORMATION

Drug supplies will be labeled in accordance with regulatory requirements. Receipt and dispensing of trial medication must be recorded by an authorized person at the trial site. Clinical supplies must be stored in a secure, limited-access location, and may not be used for any purpose other than that stated in the protocol.

14.1 Cabozantinib

14.1.1 Composition and formulation

Cabozantinib tablets are supplied by Exelixis as film-coated tablets containing cabozantinib malate equivalent to 20 mg of cabozantinib. They also contain microcrystalline cellulose, lactose anhydrous, hydroxypropyl cellulose, croscarmellose sodium, colloidal silicon dioxide, magnesium stearate and Opadry® yellow. The 20-mg tablets are round. Doses of 40 mg will comprise two 20-mg tablets. The components of the tablets are listed in Table 14.1.1.1.

Table 14.1.1.1. Cabozantinib tablet components and composition

Ingredient	Function	% w/w ¹
Cabozantinib Drug Substance (25% drug load as free base)	Active Ingredient	31.68
Microcrystalline Cellulose (Avicel® PH-102)	Filler	38.85
Lactose Anhydrous (60M)	Filler	19.42
Hydroxypropyl Cellulose (EXF)	Binder	3.00
Croscarmellose Sodium (Ac-Di-Sol®)	Disintegrant	6.00
Colloidal Silicon Dioxide	Glidant	0.30
Magnesium Stearate	Lubricant	0.75
Opadry® yellow film coating which includes HPMC 2910/hypromellose 6 cp, titanium dioxide, triacetin, and iron oxide yellow	Film Coating	4.00

¹ weight fraction, expressed in percentage; HPMC, hydroxypropyl methylcellulose

14.1.2 Storage and handling

Refer to the Pharmacy Manual for full details on storage and handling of cabozantinib. Cabozantinib tablets should be stored according to the temperature range listed on the product label and should not be crushed or chewed. Patients should store the cabozantinib capsules in the original package provided and be instructed to keep all medication out of reach of children.

14.1.3 Administration

Subjects will receive cabozantinib 20 mg oral tablets and will start at a dose of 40 mg once daily. Dosage will be adjusted for toxicity (see Section 9.0).

Cabozantinib must be taken on an empty stomach. Subjects must be instructed not to eat for at least 2 hours before and at least 1 hour after taking cabozantinib. Subjects should be instructed to take their

cabozantinib dose at approximately the same time every day. If a subject misses a dose, the dose may be taken later only if it is within 12 hours of when the missed dose should have been taken. The missed dose should not be made up if it is within 12 hours of the next scheduled dose.

Cabozantinib tablets should be swallowed whole with at least 8 ounces of water. The tablets should not be crushed.

14.1.4 Treatment accountability

Patients are required to complete the Cabozantinib Drug Diary and return all drug bottles and unused tablets. The number of tablets dispensed and returned will be recorded and reconciled with the diary.

The investigator or designee will maintain accurate records of receipt of all study treatment including dates of receipt. In addition, accurate records will be kept regarding the date, lot number, and how much study treatment is dispensed and used by each subject in the study. Reasons for deviation from the expected dispensing regimen must also be recorded. At completion of the study, to satisfy regulatory requirements regarding drug accountability, all unused study treatment will be reconciled and destroyed according to applicable state, federal, and local regulations.

14.2 Pembrolizumab

14.2.1 Formulation and preparation

Pembrolizumab is supplied by Merck in solution form for injection at a concentration of 100 mg/4 mL. Please refer to the Pharmacy Manual for a comprehensive description of pembrolizumab preparation.

14.2.2 Storage and handling

Pembrolizumab must be stored securely under storage conditions as specified on the drug label and in the Pharmacy Manual.

14.3.3 Treatment accountability

The investigator or designee is responsible for keeping accurate records of the clinical supplies of pembrolizumab received from Merck, the amount dispensed and returned for each subject, and the amount remaining at the conclusion of the trial.

Upon completion or termination of the study, all unused and/or partially used investigational product will be destroyed at the site as per institutional policy. It is the responsibility of the investigator or designee to arrange for disposal of all empty containers, following the procedures for proper disposal as per applicable federal, state, local and institutional guidelines. Records of disposed drug must be kept.

15.0 BIOLOGICAL CORRELATIVE STUDIES

15.1 Tissue collection

Archival tumor tissue will be requested, collected, and stored ambiently if available. If archival tissue is not available, an optional fresh tumor biopsy may be performed if safe and feasible. Tissue will be stored for future correlative studies in order to assess correlations of biomarkers with efficacy from cabozantinib and pembrolizumab in HCC patients.

If applicable, archival tumor tissue will be obtained from paraffin embedded specimens. Two unstained slides will be required for correlative studies. For patients undergoing fresh tumor biopsy, 3 cores will be obtained to assure at least 50 mm² of tissue needed for analysis (see below).

In addition, research blood will be collected on Cycle 1 Day 1 and Day 8 and Cycle 2 Day 1.

All samples will be coded with the patient number. These samples and any data generated can be linked back to the patient only by the study site personnel. Samples will be safely stored at -70oC until they are assayed.

Samples will be retained at the University of Washington for a maximum of 15 years after the last patient visit for the study, or for a shorter period if imposed by the IRB. This retention period enables use of new technologies, response to questions from regulatory agencies, and investigation of variable response that may not be observed until later in the development cabozantinib and pembrolizumab in HCC. Regardless of the technology utilized, data generated will be used only for the specific research scope described in this section. The correlative studies will be planned as detailed in sections 15.2-15.4.

15.2 Immunohistochemistry (IHC)

Archival or fresh tumor tissue will be immunophenotyped by a comprehensive multiplex IHC assay in the Immunopathology Core at Fred Hutchinson Cancer Center in order to detect a range of immune cell subsets and their distribution in tumor, including CD8+ and CD4+ effector T cells, regulatory T cells, macrophages, myeloid derived suppressor cells.

In addition, IHC will also be performed to assess the intratumoral levels of MET and various markers of immune checkpoint pathways (e.g. PD-1/PD-L1/PD-L2, CTLA-4, LAG3, TIM3). The intratumoral immune profile will be characterized and correlated with response to treatment.

15.3 RNA sequencing

Archival or fresh tumor tissue will be analyzed by RNA sequencing and gene set enrichment assay to explore immune gene expression signatures (e.g. IFN- γ signature, tumor inflammation signature) and activated or suppressed cell pathways that might predict response to cabozantinib and pembrolizumab. Moreover, the mutational profile and T cell receptor clonality profile of tumors will be assessed. Signatures associated with tumor response will be explored.

15.4 Flow cytometry and cytokine assays

Peripheral blood (at baseline, Cycle 1 Day 8, Cycle 2 Day 1) will be analyzed by flow cytometry for immune cell subpopulations (e.g. CD8+/CD4+/regulatory T cells, myeloid derived suppressor cells). Furthermore, serum at the same timepoints will be assayed by the Luminex® cytokine panel. Changes in immune cell subsets and cytokine profiles in response to cabozantinib and pembrolizumab will be assessed and correlated with treatment outcomes.

16.0 ADVERSE EVENT ASSESSMENT AND REPORTING

The safety of cabozantinib and pembrolizumab will be evaluated and recorded. Specifically, these are the safety endpoints of interest:

- Type, incidence, and severity grade (as defined by NCI CTCAE v5) of AEs and SAEs, as well as relatedness of AEs/SAEs to cabozantinib, pembrolizumab or both;
- AEs/SAEs leading to dose reduction;
- AEs/SAEs leading to permanent treatment discontinuation;
- Causes of death.

16.1 Definitions

Adverse event (AE): An AE is any untoward medical occurrence in a patient or clinical trial subject administered a medicinal product and which does not necessarily have a causal relationship with this treatment. An adverse event can therefore be any unfavorable and unintended sign (e.g. an abnormal laboratory finding), symptom, or disease temporarily associated with the use of a medicinal product, whether or not considered related to the medicinal product. An adverse event can arise from any use of the drug (e.g. off-label use, use in combination with another drug) and with any route of administration, formulation, or dose, including an overdose. This definition also includes AEs associated with medication errors and uses of the investigational product outside what is in the protocol, including misuse and abuse. Pre-existing medical conditions that worsen during the study should be recorded as AEs. Abnormal vital signs, ECG, physical examination, and laboratory test results will be recorded as AEs if they are CTCAE v5 grade 3 or above, require clinical intervention, or are otherwise judged clinically relevant by the investigator.

Worsening of the underlying disease is not considered an AE; however clinical events associated with worsening of disease may be reportable as AEs, including the new onset of or increase in pain.

Serious adverse event (SAE): The SAE definition and reporting requirements are in accordance with the International Conference of Harmonisation (ICH) Guideline for Clinical Safety Data Management: Definitions and Standards for Expedited Reporting, Topic E2A.

An SAE is defined as any untoward medical occurrence that at any dose:

- Results in death;

- Is life-threatening (i.e. in the opinion of the investigator, the AE places the subject at risk of death; it does not include an event that, had it occurred in a more severe form, might have caused death);
- Requires inpatient hospitalization or results in prolongation of an existing hospitalization;
 - Note: while most hospitalizations necessitate reporting of an SAE, some hospitalizations do not require SAE reporting, as follows:
 - Events that occurred during the screening period after the patient signed the consent form but before initiation of study treatment (however, events related to screening procedures should be reported as SAEs);
 - Elective or previously scheduled surgeries or procedures for pre-existing conditions that have not worsened after initiation of treatment (however, SAEs must be reported for any surgical complication resulting in unexpected prolongation of the hospital admission);
 - Events that result in hospital stays of fewer than 24 hours and that do not require admission (e.g. ER visit with diagnosis of urinary tract infection with discharge home on oral antibiotics);
 - Hospitalizations that are planned for administrative or social reasons during the study (e.g. days on which infusion takes place, long distance from home to site) will not be recorded as SAEs (however, any event that requires prolongation of a planned hospitalization will be recorded as an SAE).
- Results in persistent or significant disability or incapacity:
 - Note: The term “disability” refers to events that result in a substantial disruption of a subject’s ability to conduct normal life function.
- Is a congenital anomaly or birth defect;
- Is an important medical event (IME):
 - Note: The term “important medical event” refers to an event that, based upon appropriate medical judgment, may not be immediately life-threatening or result in death or hospitalization, but may jeopardize the subject or require intervention to prevent one of the other serious outcomes listed.
 - Examples of IMEs: intensive treatment in the ER or at home for allergic bronchospasm; blood dyscrasias, or convulsions that do not result in hospitalization; or development of product dependency or product abuse.
- Is a new cancer (other than HCC);
- Is associated with an overdose.

Unexpected: An AE that is not listed in the investigator’s brochure describing the risks of the study drug, or is not listed at the specificity or severity that has been observed.

Severity of AE: The severity of AEs will be classified according to the NCI CTCAE v5, which describes grades of severity from 1 (mild) through 5 (fatal).

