9.3.19 Endocrine disorders

Treatment-emergent elevation of thyroid-stimulating hormone (TSH) has been observed with cabozantinib monotherapy treatment. Currently available data are insufficient to determine the mechanism of thyroid function test alterations and its clinical relevance.

TSH elevation may also be related to immune-mediated endocrinopathy caused by pembrolizumab, which occurs in 8% and 5% of patients in the KEYNOTE-224 and KEYNOTE-240 trials, respectively (mostly grade 1-2).^{35,36} TSH and free T4 and T3 should be checked at least every 6 weeks (every 2 cycles) on study.

Regardless of whether it is related to cabozantinib and/or pembrolizumab, clinically symptomatic hypothyroidism should be treated with thyroxine replacement as per accepted clinical practice guidelines. See Section 9.5.5 for treatment guidelines for suspected immune-mediated endocrine AEs.

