16.4.3 Laboratory data

All laboratory data required by this protocol and any other clinical investigations should be reviewed. Any abnormal value that leads to a change in subject management (e.g. dose reduction or delay or requirement for additional medication or monitoring) or that is considered to be of clinical significance by the investigator should be reported as an AE or SAE as appropriate.

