17.2 Statistical methods

The primary endpoint is ORR per RECIST v1.1, while secondary endpoints include ORR by iRECIST, ORR and DCR by iRECIST, median PFS, and median OS. Only patients who have been on treatment with both cabozantinib and pembrolizumab concurrently for more than 42 days in the first 3 cycles (i.e. received treatment for two-thirds of the cycle) will be included in the analysis of the primary endpoint. Patients who have received any duration of study treatment will be evaluable for safety.

Binary endpoints will be summarized by percentages and associated confidence intervals. ORR will also be represented by a waterfall plot. The distribution for survival times will be estimated using the method of Kaplan-Meier; associated landmark time percentages and the median value will be based on this. Confidence intervals for median values will use the Brookmeyer-Crowley method. Any toxicity with at least 5% prevalence has at least an 77% chance of being observed among 29 patients.

For the exploratory objectives, archival or fresh tumors from all patients will be analyzed by IHC, the presence of specific immune cell subsets and protein marker expression, as well as the staining pattern and location within tumors will be described. The frequencies of immune cell subset will be obtained from flow cytometry at various timepoints, and cell changes from baseline to post-treatment timepoints will be averaged across patients. The association between immune cell, biomarker expression, gene expression signature, or cytokine level with ORR will be evaluated using Spearman correlation, where $p<0.05$ is considered significant.

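### Safety summaries rest on recorded AEs alone, so the incidence of asymptomatic grade 1-2 laboratory changes depends on investigator judgement; section 17.2 should add program-graded laboratory tables

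*Combined protocol and SAP*

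**What the plan says.** The safety endpoints in section 16.0 are built on adverse events. The first is "Type, incidence, and severity grade (as defined by NCI CTCAE v5) of AEs and SAEs"; the others are relatedness, AEs leading to dose reduction or discontinuation, and causes of death. No endpoint is defined on laboratory values.

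Two sections decide when an abnormal result becomes an AE:

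- Section 16.1 covers vital signs, ECG, physical examination and laboratory results. It gives three routes. Two are set out in these words: "laboratory test results will be recorded as AEs if they are CTCAE v5 grade 3 or above, require clinical intervention". The third is the investigator's own view that the result matters clinically.
- Section 16.4.3 covers laboratory data only. It asks for reporting of "Any abnormal value that leads to a change in subject management (e.g. dose reduction or delay or requirement for additional medication or monitoring"), and of any value the investigator considers clinically significant. It has no grade threshold.

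Section 17.2 says "Patients who have received any duration of study treatment will be evaluable for safety" and adds: "Any toxicity with at least 5% prevalence has at least an 77% chance of being observed among 29 patients". It names no worst-grade table, shift table or other summary of laboratory values.

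The values themselves are scheduled. Table 10.1 and section 11.2 require blood count, chemistry and coagulation tests every cycle, and TSH, cortisol, amylase, lipase, UPCR and EKG every two cycles from cycle 3.

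**The concern.** Safety of the combination is a stated secondary objective, and several of the harms the protocol expects show up first in the laboratory: transaminase elevation, thyroid change, proteinuria and low platelets. Many are mild. Section 9.3.19 describes the thyroid effects seen with pembrolizumab as mostly grade 1-2, and says of cabozantinib that "Currently available data are insufficient to determine the mechanism of thyroid function test alterations and its clinical relevance".

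Below grade 3 and without an intervention, an abnormal value reaches the safety tables only if it changes management or an investigator judges it relevant. The two sections word this differently, so two investigators could treat the same value differently and both be following the protocol. With no analysis of the values themselves, nothing in the plan would reveal the difference.

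At stake is the interpretation of low-grade laboratory incidence in a single-arm trial of 29 patients, where moving two or three patients changes a rate by 7 to 10 percentage points (2/29 = 6.9%, 3/29 = 10.3%).

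**Working it through.** **1. The plan's own figure.** Section 17.2 gives 29 patients, 5% prevalence and 77%. The chance of at least one case is 1 - (1 - 0.05)^29 = 0.774. The stated 77% reproduces.

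**2. What the recording rules already capture below grade 3.**

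- Liver: section 9.5.3 asks for liver tests at least weekly when abnormal liver tests indicate liver toxicity, against every three weeks on schedule from cycle 2. That is extra monitoring, so 16.4.3 applies. No grade is given.
- Thyroid: Table 9.5.5.1 starts hormone replacement for grade 2-4 hypothyroidism, which is an intervention under 16.1.
- Urine protein: section 9.3.9 asks for more frequent UPCR testing if abnormal.

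**3. What they leave to judgement.**

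- Grade 1-2 hematologic events: Table 9.5.1.1 prescribes no modification of either drug.
- UPCR up to 1 mg/mg: Table 9.3.9.1 changes neither treatment nor monitoring.
- Grade 1 TSH elevation without symptoms: neither section 9.3.19 nor Table 9.5.5.1 calls for replacement.
- Mild transaminase change that is not taken to indicate liver toxicity. Inclusion criterion 10d admits ALT/AST up to 5 x ULN, so some patients may start abnormal.

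**4. How much of a known toxicity lies below grade 3.** These are the AST rates cited in sections 1.2.5, 1.4.1.5 and 1.4.2.2, with expected patients = rate x 29.

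| Cited trial | Any grade | Grade 3-4 | Below grade 3 | Expected in 29 |
|---|---|---|---|---|
| Cabozantinib phase 3 | 22% | 12% | 10 points | 6.4 vs 3.5 |
| Pembrolizumab phase 2 | 14% | 7% | 7 points | 4.1 vs 2.0 |
| Pembrolizumab phase 3 | 9% | 5% | 4 points | 2.6 vs 1.5 |
| Lenvatinib/pembrolizumab phase 1b | 27% | 17% (grade 3 only) | at most 10 points | 7.8 vs 4.9 |

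About one to three patients per trial-sized sample fall below the automatic threshold. This illustrates the size of the low-grade share. It does not estimate the bias, because step 2 captures some of these patients and the cited rates are themselves AE-based.

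**5. Detection under incomplete recording.** Let p be the true prevalence and s the share recorded. Detection = 1 - (1 - p x s)^29. The documents give no s, so the values are assumed.

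- p = 5%: s = 1 gives 77.4%; 0.9 gives 73.7%; 0.75 gives 67.0%; 0.5 gives 52.0%; 0.25 gives 30.6%.
- Hypothyroidism at 8% (pembrolizumab phase 2): 91.1% if all recorded, 69.4% if half. It stays at 77.4% or more if s is at least 0.05/0.08 = 0.625.
- Hypothyroidism at 5% (pembrolizumab phase 3): 77.4% if all recorded, 52.0% if half.

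**6. AST if only grade 3-4 events were recorded.** At 12%: 97.5%. At 7%: 87.8%. At 5%: 77.4%. Detection stays at 77% or above on each of these rates.

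**The case against.** The strongest reply is that the recording rules are wider than the grade 3 threshold suggests. Section 16.1 has the investigator-relevance route, 16.4.3 has no grade floor and includes extra monitoring, and 9.1 has all AEs and changes in pre-existing conditions documented. Section 16.5.4 also makes combined transaminase and bilirubin elevation with low ALP a reportable event. This stands. The gap is confined mainly to incidental low-grade change without consequence, and does not extend to any-grade liver and thyroid toxicity in general.

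A reader might go further in three ways that the documents do not support:

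- *That low-grade laboratory toxicity is under-reported.* No recorded share is given, so this is a risk and not a finding.
- *That the 77% statement fails for laboratory toxicities.* The arithmetic is right, and the figure is the chance of at least one case, which does not require complete counts. For AST it survives on grade 3-4 events alone.
- *That the results cannot be set against the rates cited for other trials.* Those rates are reported as treatment-emergent or treatment-related AEs, and the protocol does not say how those trials recorded laboratory findings. Program-derived grades would be a different measure and not obviously closer to them.

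It is also fair to say that safety here is descriptive, and that no test or stopping rule uses any-grade laboratory incidence. That limits the weight of the point. It does not remove the reason for a summary that can be made from tests already required.

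**Conclusion.** The point holds in a limited form. For asymptomatic grade 1-2 laboratory changes that alter nothing in management, the reported incidence depends on investigator judgement under two differently worded triggers, and no planned analysis of the values would correct for it. Any bias would be downward, and its size cannot be estimated from the documents.

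The 77% sentence needs a qualifier, not a new number. It is not ensured where true prevalence is near 5% and recording is incomplete: 67% to 31% for assumed recording shares of 75% to 25%. The primary endpoint and the two-stage design are untouched. The change is worth making because it removes discretion from part of a stated secondary objective at small cost.

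**What to change.** 1. Reconcile the recording triggers in 16.1 and 16.4.3, so that one rule decides when an abnormal result is an AE.
2. Add to 17.2: for all treated patients, CTCAE v5 grades are derived by program from the protocol-scheduled laboratory values. Report the worst post-baseline grade and a baseline-to-worst-grade shift table for blood count, ALT, AST, ALP, bilirubin, albumin, INR, creatinine, electrolytes, amylase and lipase, with baseline-to-worst category shifts for TSH, UPCR and QTcF. State how abnormal baselines are handled.
3. Present these tables beside the investigator-reported AEs and label them separately, since they are different measures.
4. Confirm that the scheduled values are captured on the CRF. Section 19.4 limits entry to what the CRFs require and does not say whether these values are included.
5. State that the 77% sentence applies to toxicities that are fully recorded.

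No new visits or tests are needed, and no dose or management rule changes. The cost is some table programming, possibly laboratory data entry, and any-grade laboratory rates that may look less favourable.
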